9.5.1.5.2 SERIOUS ADVERSE EVENTS AND EVENTS ASSOCIATED WITH SPECIAL SITUATIONS

A serious adverse event (SAE) is any untoward medical occurrence that at any dose:

- Results in death
- Is life-threatening (ie, the subject was at immediate risk of death from the AE as it occurred; this does not include an event that, had it occurred in a more severe form or was allowed to continue, might have caused death)
- Requires inpatient hospitalization or prolongation of existing hospitalization
- Results in persistent or significant disability/incapacity
- Is a congenital anomaly/birth defect (in the child of a subject who was exposed to the study drug)

Other important medical events that may not be immediately life-threatening or result in death or hospitalization but, when based on appropriate medical judgment, may jeopardize the subject or may require intervention to prevent one of the outcomes in the definition of SAE listed above should also be considered SAEs. Medical and scientific judgment should be exercised in deciding whether expedited reporting is appropriate in such situations.

In addition to the above, events associated with special situations include pregnancy or exposure to study drug through breastfeeding; AEs associated with study drug overdose, misuse, abuse, or medication error. These events associated with special situations are to be captured using the SAE procedures but are to be considered as SAEs only if they meet one of the above criteria. All AEs associated with special situations are to be reported on the CRF whether or not they meet the criteria for SAEs.

All SAEs must be followed to resolution or, if resolution is unlikely, to stabilization.

The following hospitalizations are not considered to be SAEs because there is no "adverse event" (ie, there is no untoward medical occurrence) associated with the hospitalization:

- Hospitalizations for respite care
- Planned hospitalizations required by the protocol
- Hospitalization planned before informed consent (where the condition requiring the hospitalization has not changed post study drug administration)

- Hospitalization for administration of study drug or insertion of access for administration of study drug
- Hospitalization for routine maintenance of a device (eg, battery replacement) that was in place before study entry

If possible, a blood sample for PK analysis should be drawn at the first report of an SAE or a severe unexpected AE and at its resolution.

9.5.1.5.3 LABORATORY MEASUREMENTS

Clinical laboratory tests to be performed, including hematology, chemistry, and urinalysis, are summarized in Table 3. Subjects should be in a seated or supine position during blood collection and are to be fasting for at least 4 hours before blood is drawn for clinical laboratory measurements. The Schedule of Procedures/Assessments (Table 4) shows the visits and time points at which blood for clinical laboratory tests and urine for urinalysis will be collected in the study.

Table 3 Clinical Laboratory Tests					
Category	Parameters				
Hematology	Hematocrit, hemoglobin, platelets, red blood cell (RBC) count, and white blood cell (WBC) count with differential (bands, basophils, eosinophils, lymphocytes, monocytes, neutrophils)				
Coagulation Panel	Prothrombin time (PT), activated partial thromboplastin time (aPTT), and international normalized ratio (INR)				
Chemistry					
Electrolytes	Chloride, potassium, sodium, calcium				
Liver function tests	Alanine aminotransferase, alkaline phosphatase, aspartate aminotransferase, gamma glutamyl transpeptidase, direct bilirubin, total bilirubin				
Other	Total protein, globulin, albumin, cholesterol, triglycerides, glucose, lactate dehydrogenase, uric acid, and creatinine (revised per Amendment 01)				
Urinalysis	Bacteria, casts, crystals, epithelial cells, glucose, ketones, occult blood, pH, protein, RBCs, specific gravity, WBCs				
Virology	Hepatitis B surface antigen (HBsAg) and hepatitis C antibody (HCVAb)				

Clinical laboratory tests during the study will be performed by a Clinical Laboratory Improvement Amendments (CLIA) certified laboratory. All blood and urine samples will be collected and sent to the central laboratory on the day of collection unless otherwise instructed. A laboratory abnormality may meet the criteria to qualify as an AE as described in this protocol (see Section 9.5.1.5.1) and the CRF Completion Guidelines. In these instances, the AE corresponding to the laboratory abnormality will be recorded on the Adverse Event CRF.

9.5.1.5.4 VITAL SIGNS AND WEIGHT MEASUREMENTS

Vital sign measurements (ie, systolic and diastolic blood pressure [BP] [mmHg], pulse [beats per minute], respiratory rate [per minute], body temperature [in centigrade]), and weight (kg) will be obtained as designated in the Schedule of Procedures/Assessments (Table 4) by a validated method. Blood pressure and pulse will be measured after the subject has been in supine position for 5 minutes. All BP measurements should be performed on the same arm, preferably by the same person.

When vital signs are to be obtained concurrently with PK or other blood samples, the vital sign measurements will be performed prior to drawing blood samples in order to maximize the accuracy of blood sampling times while minimizing the potential effects of blood drawing on recordings obtained during safety assessments.

9.5.1.5.5 PHYSICAL EXAMINATIONS

Comprehensive and abbreviated physical examinations will be performed as designated in the Schedule of Procedures/Assessments (Table 4). Documentation of the physical examination will be included in the source documentation at the site. Significant findings at the Screening Visit will be recorded on the Medical History and Current Medical Conditions CRF. Changes from screening physical examination findings that meet the definition of an AE will be recorded on the Adverse Events CRF.

Comprehensive Physical Examination

A comprehensive physical examination will include evaluations of the head, eyes, ears, nose, throat, neck, chest (including heart and lungs), abdomen, limbs, skin, and a complete neurological examination. The subject will be queried regarding physical status and subjective symptoms as well.

Abbreviated/Routine Physical Examination

Health status will be assessed by brief evaluation of the chest (including heart and lungs), abdomen and limbs, and other physical conditions of note. The subject must be queried regarding changes in physical status since the last examination.

9.5.1.5.6 ELECTROCARDIOGRAMS

Twelve-lead electrocardiograms will be obtained as designated in the Schedule of Procedures/Assessments (Table 4).

An ECG abnormality may meet the criteria of an AE as described in this protocol (see Section 9.5.1.5.1) and the CRF Completion Guidelines. In these instances, the AE corresponding to the ECG abnormality will be recorded on the Adverse Events CRF.

9.5.1.5.7 VIRAL TESTS

An 8.5 mL sample of blood will be taken for hepatitis B surface antigen (HBsAg) and hepatitis C antibody (HCVAb) at Screening.

9.5.1.5.8 PREGNANCY TEST

At Screening, a serum pregnancy (β -hCG test) will be performed for all premenopausal women and postmenopausal women who have been amenorrheic for less than 12 months using the 8.5 mL blood sample taken for clinical laboratory tests. These women will have a urine pregnancy test after Screening at the designated time points specified in the Schedule of Procedures/Assessments (Table 4).

9.5.1.5.9 URINE DRUG TEST

A 30-mL urine sample will be collected at designated time points as specified in the Schedule of Procedures/Assessments (Table 4). This sample will be tested for common drugs of use/abuse: eg, cocaine, cannabinoids, PCP, opioids (as a group), benzodiazepines, barbiturates, and amphetamines.

9.5.1.5.10 BREATH ALCOHOL TEST

The breath alcohol test will be performed according to the investigational site's SOP at designated time points as specified in the Schedule of Procedures/Assessments (Table 4).

9.5.2 Schedule of Procedures/Assessments

9.5.2.1 Schedule of Procedures/Assessments

Table 4 presents the schedule of procedures/assessments for the study.

Table 4 Schedule of Procedures/Assessments in E2006-A001-104									
Study Phase	Prerandomization		Treatment						
Period	Screening	Baseline							
Visit	1			2			3	4	5/Early Discontinuation
Day(s)	-21 to -2	-1	1	2	3, 4, 5, 6, 7	8	10	12	Day 14/ET
Assessment									
Informed Consent	Х								
Inclusion/Exclusion Criteria	Х	Х							
Medical History and Demographics	Х								
Comprehensive Physical Exam	Х								
Abbreviated/Routine Physical Exam		Х				Х			Х
Height, Weight, and BMI	Х	X ^a :							
Vital Signs ^b :	Х	Х	Х	X		Х	Х	Х	Х
12-lead ECG ^{c:}	Х	X	Х	X					Х
Viral Screen (hepatitis B and C)	Х								
Urine Drug Test	Х	Х							
Alcohol Breathalyzer	Х	Х							
Serum β -hCG Pregnancy Test ^{d:}	Х								
Urine Pregnancy Test ^{d:}		Х							Х
Clinical Lab Tests (Hematology, Clinical	V	V		v					V
Chemistry, and Urinalysis) ^{e:}	А	А		А					A
PT, aPTT, and INR	Х	Х		Х					Х
PK Blood Sample ¹			Х	Х	Х	Х	Х	Х	Х
Blood Sample for Protein Binding			v	v					
Assessment ^{g:}			А	А					
Administer Lemborexant h:			Х						
Admission to Clinic		Х							
Release from Clinic ¹						Х			
Discharge from Study ^{j:}									Х
Adverse Events	←								
Prior/Concomitant Medications	≤ ←								
aPTT=activated partial thromboplastin time; β -hCG= beta-human chorionic gonadotropin; BMI=body mass index; ECG = electrocardiogram; ET= early									

termination; INR= international normalized ratio; PK=pharmacokinetic; PT=prothrombin time

- a: Only weight will be recorded at Baseline (Day -1).
- b: Single measurements of vital signs (blood pressure, heart rate, body temperature, and respiratory rate) after at least 5 minutes of supine rest will be recorded at Screening, clinic check-in on Day -1, predose on Day 1, Day 2, prior to clinic discharge on Day 8, on Days 10 and 12, and at end-of study (Day 14 or early termination).
- c: Single ECG will be recorded at Screening, Baseline (Day -1), Day 1 (predose and 3 hours postdose), Day 2 (24 hours postdose), and Day 14 (312 hours postdose). A variance of ± 15 minutes is allowed. Before excluding a subject with QTcF > 480 at Screening, ECG should be repeated once to confirm.
- d: Females of childbearing potential only.
- e: Subjects will fast for at least 4 hours before blood is drawn for clinical laboratory assessments. Measurement of serum albumin and creatinine will be part of the central laboratory tests. (revised per Amendment 01)
- f: Blood samples (4 mL per time point) for PK assessments will be collected on Day 1 (predose and at 0.5, 1, 1.5, 2, 3, 4, 6, 8, and 12 hours postdose), Days 2 (24 hours postdose), 3 (48 hours postdose), 4 (72 hours postdose), 5 (96 hours postdose), 6 (120 hours postdose), 7 (144 hours postdose), 8 (168 hours postdose), 10 (216 hours postdose), 12 (264 hours postdose) and 14 (312 hours postdose). If a subject is early terminated, he or she will not have a blood sample collected for PK unless early termination coincides with a scheduled PK time point. A variance of ±5 minutes (up to the first 2 hours postdose), ±10 minutes for time points up to, and including, Day 8 (168 hours postdose) and ±2 hours for Day 10 (216 hours postdose) to Day 14 (312 hours postdose) is allowed.
- g: Blood samples (12 mL per time point) for plasma protein binding will be collected at approximately 1 and 24 hours postdose, matching with the time collection for PK samples for lemborexant and its main metabolite, M4, M9 and M10.
- h: A single 10-mg dose of lemborexant as 1×10 mg tablet will be administered with 240 mL of water following an overnight fast. Dosing will be in the morning followed by a 4-hour postdose fast. Water will be allowed ad libitum except for the interval from 1 hour before to 1 hour after study drug administration.
- i: Subjects will be released from the clinic after completing the Day 8 procedures and then return to the clinic for outpatient visits on Days 10, 12, and 14.
- j: Subject will be released from the study after completion of Day 14 (end-of-study) procedures or early termination.

Table 5	ble 5 Blood Sampling Schedule for Pharmacokinetic Assessments					
Study day	Time (on each day) Acceptable time-window					
Day 1	Predose and at 0.5, 1, 1.5, 2, 3, 4, 6, 8, and 12 hours postdose	Predose; -1 hour Postdose (up to first 2 hours postdose); ±5 minutes				
		Postdose (after 2 hours postdose); ±10 minutes				
Day 2	24 hours postdose					
Day 3	48 hours postdose					
Day 4	72 hours postdose					
Day 5	96 hours postdose	±10 minutes				
Day 6	120 hours postdose					
Day 7	144 hours postdose					
Day 8	168 hours postdose					
Day 10	216 hours postdose					
Day 12	264 hours postdose	±2 hours				
Day 14	312 hours postdose					

Table 5 presents the blood sampling schedule for PK assessments.

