With lemborexant as the only pharmacologically active moiety, the primary PK endpoints for the study will be the total C_{max} and AUC parameters for lemborexant, whereas the PK comparisons for the metabolites will be secondary endpoints. In order to account for potential prolongation of the half-life of lemborexant or metabolites in subjects with liver impairment, the PK samples will be collected up to Day 14 after dosing. One of the key assessments stipulated in all regulatory guidelines for special population studies (ie, renal and hepatic impairment) is the evaluation of any change in the unbound fraction of the pharmacologically active moieties in vivo and assessment of the relationship between the unbound plasma exposures (AUC_u) and apparent clearance with measures of liver impairment, where binding of the drug to plasma proteins is high (eg. >90%). With lemborexant and its main metabolites (M4, M9, and M10), plasma protein binding based on in vitro studies is approximately 88%, 74%, 86%, and 92% bound to human plasma, respectively, and linear over the clinically observed concentrations. Due to the marginally high plasma protein binding of lemborexant and its metabolites in the current study, 2 blood samples will be collected, one at the maximum plasma exposure time and one at trough level. The respective unbound PK parameters for lemborexant will be derived by applying the unbound ratio to the PK parameters calculated using total plasma concentrations of lemborexant. Plasma protein binding of metabolites will be assessed to compare these results to in vitro data and assess any difference between hepatic impaired subjects and healthy volunteers that is currently not anticipated. The analysis of the unbound PK parameters (lemborexant only) between subjects with liver impairment and normal controls will be considered as secondary PK parameter endpoints only.

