9.5.2.2 Total Volume of Blood Sampling

Table 6 presents the number of blood samples and the total volume of blood that will be collected throughout the study. Additional samples may be taken at the discretion of the investigator if the results of any tests fall outside reference ranges or clinical symptoms necessitate testing to ensure subject safety.

Table 6	Summary of Blood Sample Volumes
---------	---------------------------------

	Sample Volume per Collection (mL)	Number of Collection Time Points	Total Volume Collected (mL)
Clinical laboratory tests	8.5	Screening (including pregnancy testing): 1 Baseline (Day -1): 1 Day 2: 1 Day 14 or early termination: 1	8.5×4=34
Viral test	8.5	Screening: 1	8.5×1=8.5
PK blood sampling	4	20	4×20=80
Blood sampling for plasma protein binding	12	2	2×12=24
Total			146.5

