9.5.5 Completion/Discontinuation of Subjects

The investigator may withdraw the subject from the study at any time for safety or administrative reasons. A subject may elect to discontinue the study at any time for any reason. All subjects who discontinue the study are to complete the study's early discontinuation procedures indicated in the Schedule of Procedures/Assessments (Table 4).

The investigator will promptly explain to the subject involved that the study will be discontinued for that subject and provide appropriate medical treatment and other necessary measures for the subject. A subject who has ceased to return for visits will be followed up by mail, phone, or other means to gather information such as the reason for failure to return, the status of treatment compliance, the presence or absence of AEs, and clinical courses of signs and symptoms.

Subjects who discontinue early from the study will be discontinued for 1 of these primary reasons: AE(s), lost to follow-up, subject choice, withdrawal of consent, pregnancy, study terminated by sponsor, or other. In addition to the primary reason, the subject may indicate 1 or more of secondary reasons for discontinuation. Study disposition information will be collected on the Subject Disposition CRF.

A subject removed from the study for any reason may be replaced.

9.5.6 Confirmation of Medical Care by Another Physician (for Hepatic Impairment Subjects):

The investigator will instruct subjects to inform site personnel when they are planning to receive medical care by another physician. At each visit, the investigator will ask the subject whether he/she has received medical care by another physician since the last visit or is planning to do so in the future. When the subject is going to receive medical care by another physician, the investigator, with the consent of the subject, will inform the other physician that the subject is participating in the clinical study.

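### Table 4 footnote f forgoes one usable late concentration from a subject who leaves off schedule, and makes no exception for the PK sample requested at an SAE

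*Protocol*

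**What the plan says.** - **The rule.** Under Table 4 footnote f, a subject who terminates early gets no PK tube off schedule: "he or she will not have a blood sample collected for PK unless early termination coincides with a scheduled PK time point". Table 5 and the same footnote set the tolerance at ±10 minutes up to 168 h (±5 minutes in the first 2 h) and ±2 h at 216, 264 and 312 h.
- **The visit.** Protocol 9.5.5 makes an exit visit the norm: "All subjects who discontinue the study are to complete" the early-discontinuation procedures of Table 4. Those sit in a column shared with Day 14 and headed "5/Early Discontinuation". The clinical laboratory, coagulation and PK rows are all marked there. Table 6 confirms the laboratory draw: "Day 14 or early termination: 1".
- **The SAE sample.** Protocol 9.5.1.5.2 says that, if possible, "a blood sample for PK analysis should be drawn at the first report of an SAE or a severe unexpected AE", and again at resolution. It mentions no scheduled times.
- **Why sampling runs to Day 14.** Protocol 7.2.3 gives the reason: "In order to account for potential prolongation of the half-life of lemborexant or metabolites" in liver impairment.
- **The analysis.** SAP 6.3.1 refers in passing to actual sampling time as the basis for PK parameters. SAP 6.15 tabulates concentrations by nominal time. SAP 6.2.3 leaves AUC(0-inf) out of the summary statistics when more than 20% is extrapolated, unless the sponsor approves. It sets no such limit for AUC(0-t).

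**The concern.** A needle is already in the arm at the exit visit, and non-compartmental analysis can use a concentration at any recorded time. Refusing the PK tube therefore saves almost nothing and gives up the latest point available for that subject. The point would extend AUC(0-t), lengthen the λz window and reduce the extrapolated part of AUC(0-inf). Two of these, AUC(0-t) and AUC(0-inf), are primary endpoints in cohorts of 8. Early leavers stay in the PK Analysis Set if one parameter can be derived, so a shortened AUC(0-t) goes into the primary model as it stands.

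There is also an operational problem. If the SAE is first reported, or resolves, at an exit visit that falls off schedule, 9.5.1.5.2 asks for a PK sample and footnote f refuses it.

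**Working it through.** **1. The plan's own precision figure.** Inputs (Protocol 9.7.2): SD of log AUC(0-inf) 0.391, 8 per group, two-sided 90% CI.
- Normal quantile: 1.645 × 0.391 × √(1/8 + 1/8) = 1.645 × 0.1955 = 0.322, as stated.
- t quantile for the three-group model (24 − 3 = 21 df): 0.336.
- One AUC(0-inf) value lost and not replaced (7 versus 8, 20 df): t × 0.391 × √(1/7 + 1/8) = 0.349. The widening is 0.349/0.336, about 4%. With the normal quantile it is 0.322 to 0.333.

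**2. How often an exit visit could qualify.**
- From 24 to 168 h the windows cover 20 minutes in every 24 h, or 1.4% of clock time.
- From 168 to 312 h they cover (4 + 4 + 2)/144 = 6.9%.
- An exit at 192, 240 or 288 h (Days 9, 11 and 13) falls outside every window.

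These are shares of clock time, not probabilities of exit.

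**3. What one exit sample adds.** If earlier scheduled visits were attended, the gap it fills is under 24 h between 24 and 168 h and under 48 h afterwards. Cmax is unaffected once the peak has passed (about 1 to 3 h, Protocol 7.1.1.2).

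**4. Effect on the 20% rule.** Assume mono-exponential decline, so the extrapolated share after last sample time t is 2^(−t/t½). This is an upper bound, because a faster early phase lowers the share. Half-lives are from Protocol 7.1.1.2: 50 h lies within the healthy range of 45 to 55 h, and 118 h is the itraconazole value, used here as an assumed stand-in for a prolonged case.

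| t½ | Last scheduled sample | Exit just before | Share without exit sample | Share with it (limit) |
|---|---|---|---|---|
| 118 h | 264 h | 312 h | 21.2% | 16.0% |
| 118 h | 216 h | 264 h | 28.1% | 21.2% |
| 118 h | 168 h | 216 h | 37.3% | 28.1% |
| 50 h | 96 h | 120 h | 26.4% | 18.9% |
| 50 h | 168 h | 216 h | 9.7% | 5.0% |

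The share reaches 20% at t = t½ × ln 5/ln 2, which is 274 h for 118 h and 116 h for 50 h. The exit sample therefore decides the rule only for exits from about 274 h until the 312 h window opens at 310 h (half-life 118 h), or from about 116 h until just before 120 h (half-life 50 h).

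**5. The λz span.** SAP 6.2.3 also weighs whether the λz range covers two half-lives.
- At 118 h that is 236 h. The fit must start by 264 − 236 = 28 h without the exit sample, or by 312 − 236 = 76 h with it.
- At 50 h it is 100 h. This cannot be met with a last sample at 96 h. With the exit sample the fit must start by 120 − 100 = 20 h.

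The exit point helps, but does not guarantee a reportable AUC(0-inf).

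**6. Effect on AUC(0-t).** Under the same bound, the captured share rises from 78.8% to 84.0% (118 h, exit near 312 h) or from 73.6% to 81.1% (50 h, exit near 120 h). For one subject in a cohort of 8, the log geometric mean moves by ln(84.0/78.8)/8 = 0.008 or ln(81.1/73.6)/8 = 0.012, that is, by about 1%.

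**The case against.** The strongest reply is that this is a deliberate choice with little consequence. Every scheduled concentration before exit is kept, replacement is allowed in all cohorts (Protocol 9.5.5), and the 20% rule can be waived by the sponsor. Subjects are confined to Day 8 and then attend on PK days, so exits at arbitrary times may be few, and those lost to follow-up give no sample under any rule. The request in 9.5.1.5.2 is conditional and triggered by the event, so it already provides off-schedule samples for some leavers. All of this stands, and it limits the size of the point. It gives no reason for refusing the tube and does not supply the missing exception in footnote f.

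Three stronger readings are tempting, and the documents do not support them.
- *Collected data are thrown away.* They are not. The tube is never drawn, and AUC(0-t) runs to the last quantifiable concentration obtained.
- *Table 4 contradicts itself.* The PK mark is in a column shared by Day 14 and early termination, and footnote f, attached to that row, says when the mark applies at early termination.
- *The loss falls on the impaired cohorts and biases the primary ratios.* This depends on exit time. At 168 h the bound is 37.3% for a half-life of 118 h and 11.6% for 54 h, so late exits matter more when half-life is long. For exits before Day 8 the 20% rule can turn for a half-life of 50 h, but not for 118 h, where the share stays above 20% until about 274 h.

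**Conclusion.** The point holds as a minor, cheap improvement. Footnote f gives up at most one later concentration per off-schedule leaver, without an analytic reason, and it needs to be reconciled with 9.5.1.5.2. The gain is confined to AUC(0-t), λz and AUC(0-inf). It changes the status of AUC(0-inf) under the 20% rule only for particular exit times, and in the examples it moves a cohort's geometric mean AUC(0-t) by about 1%. These sizes rest on mono-exponential decline and on 118 h as an assumed prolonged half-life. The step from 0.336 to 0.349 further assumes that one value is lost entirely and not replaced. The documents give no dropout rate, so the number of subjects affected is unknown; the overall effect is probably small.

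**What to change.** - **Protocol, Table 4 footnote f.** Replace the early-termination sentence with: *At early termination a 4 mL PK sample is collected with the exit laboratory blood, at whatever time the visit occurs, and the actual time is recorded.* Add a cross-reference to 9.5.1.5.2 so that sites have one consistent instruction.
- **SAP 6.2.3 and 6.15.** Confirm that exit samples enter the non-compartmental analysis at actual time and are left out of the nominal-time concentration summaries. SAP 6.3.1 and 6.15 already point this way, so one line is enough.

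**Cost.** One sentence of amendment, one tube per early leaver at an existing blood draw, and a few off-schedule concentrations to handle. Table 6 totals 34 + 8.5 + 80 + 24 = 146.5 mL. A subject who leaves before the 312 h sample has missed at least one scheduled 4 mL tube, so the exit tube does not take that subject above this total.
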